3.4. Justification of the Study Design

Goals of Phase 1 studies include establishment of an MTD and determination of a recommended range of doses for evaluation in future clinical studies based on PK and pharmacodynamic effects [54,55,56]; the primary objectives of the current study are consistent with those typical of Phase 1 studies.

The Phase 1b segment of the study will employ a standard 3+3 dose escalation design, the most common dose escalation method for conducting Phase 1 oncology studies.[57] The minimum number of patients to be treated at each dose level is consistent with this standard dose escalation design. In order to ensure the safety of patients, an SRC consisting of Sponsor personnel including the Sponsor Medical Monitor, the Sponsor Safety Monitor, and Investigators will review safety data from all patients enrolled in each dose cohort to confirm any DLTs that were experienced and make a determination regarding enrollment in the next dose cohort.

Sparse PK sampling in Phase 2 will be analyzed to determine relationship of drug exposure to response and potential adverse events.

3.5. Study Termination

If the Sponsor or Investigator discovers conditions arising during the study that suggest the study should be halted, then study termination can occur only after appropriate consultation between the Sponsor and Investigators. Conditions that may warrant study termination include, but are not limited to:

- The discovery of any unexpected, significant, or unacceptable risk to the patients enrolled in the study.
- Failure of the Investigator to enter patients at an acceptable rate.
- Insufficient adherence to the protocol requirements.
- A decision on the part of the Sponsor to suspend or discontinue development of study drug.

Should the study be closed prematurely, all study materials must be returned to the Sponsor or designee.

4. STUDY POPULATION

4.1. Number of Patients

Based on the dose escalation scheme, a total of up to 125 patients are planned to be enrolled, including up to 30 patients in the Phase 1b segment and up to 95 patients in the Phase 2 segment.

4.2. Inclusion Criteria

Patients meeting all of the following criteria are to be enrolled in the study.

1. Must be able to understand and voluntarily sign an informed consent form (ICF).
2. Must be registered into the mandatory POMALYST REMSTTM program, and be willing and able to comply with the requirements of the POMALYST REMSTTM program (or RevAid[®] for study participants in Canada).
3. Must be ≥ 18 years of age at the time of signing the ICF.
4. Must be able to adhere to the study visit schedule and other protocol requirements.
5. Must have a documented diagnosis of MM and have relapsed-and-refractory disease. Patients must have received at least 2 lines of prior therapies. Patients must have **relapsed** after having achieved at least SD for at least one cycle of treatment to at least one prior regimen and then developed PD. Patients must also have documented evidence of PD during or within 60 days (measured from the end of the last cycle) of completing treatment with the last anti-myeloma drug regimen used just prior to study entry (**refractory disease**).
6. Must have undergone prior treatment with at least 2 cycles of lenalidomide and at least 2 cycles of a proteasome inhibitor (either in separate regimens or within the same regimen).
7. Must not be a candidate for autologous stem cell transplant (ASCT), has declined the option of ASCT, or has relapsed after prior ASCT.
8. Must have measurable levels of myeloma paraprotein in serum (≥ 0.5 g/dL) or urine (≥ 0.2 g/24 hours). Nonsecretory myeloma and SFLC-only myeloma are excluded.
9. Must have Eastern Cooperative Oncology Group (ECOG) performance status score of 0, 1, or 2.
10. FCBP must have a negative serum or urine pregnancy test (must be serum for study participants in Canada), as described in Appendix 9.3 for the POMALYST REMSTTM program (in the US) and Appendix 9.4 for the RevAid[®] program (in Canada) FCBP and males must either commit to continued abstinence from heterosexual intercourse or must abide by birth control requirements as described in Appendix 9.3 for the POMALYST REMSTTM program (in US) and Appendix 9.4 for the RevAid[®] program (in Canada). The European Pomalidomide Pregnancy Prevention Risk Management Plans are described in Appendix 9.5.
11. Must agree to refrain from donating blood while on study drug and for 28 days after discontinuation from this study.
12. Must agree not to share study medication with another person.
13. Must be able to take acetylsalicylic acid (ASA) (81 or 325 mg) daily as prophylactic anticoagulation. Patients intolerant to ASA may use low molecular weight heparin.

Lovenox is recommended. Coumadin will be allowed provided the patient is fully anticoagulated, with an international normalized ratio (INR) of 2 to 3.

4.3. Exclusion Criteria

Patients meeting any of the following criteria will be excluded from enrollment in the study:

1. Any serious medical condition, laboratory abnormality, or psychiatric illness that would prevent the patient from signing the ICF, including nonsecretory myeloma or SFLC-only myeloma.
2. Any serious concurrent medical conditions, laboratory abnormality, or psychiatric illness that might make the patient non-evaluable, put the patient's safety at risk, or prevent the patient from following the study requirements.
3. Pregnant or lactating females.
4. Prior therapy with HDAC inhibitor or pomalidomide.
5. Any of the following laboratory abnormalities:
 - ANC < 1,000/ μ L (hematopoietic growth factors will not be permitted during screening in the Phase 1 or Phase 2 segments of the study or in Cycle 1 of the Phase 1b segment of the study).
 - Platelet count < 75,000/ μ L for patients in whom < 50% of bone marrow nucleated cells are plasma cells, and < 50,000/ μ L for patients in whom \geq 50% of bone marrow nucleated cells are plasma cells
 - Hemoglobin < 8 g/dL (< 4.9 mmol/L; prior RBC transfusion is permitted)
 - Creatinine clearance < 45 mL/min according to Cockcroft-Gault formula. If creatinine clearance calculated from the 24-hour urine sample is \geq 45 mL/min, patient will qualify for the study.
 - Serum glutamic oxaloacetic transaminase (SGOT)/aspartate aminotransferase (AST), or serum glutamic pyruvic transaminase (SGPT)/ALT $>$ 3.0 \times upper limit of normal (ULN).
 - Serum total bilirubin $>$ 2.0 mg/dL
6. Prior history of malignancies, other than MM, unless the patient has been free of the disease for \geq 3 years. Exceptions include the following:
 - Basal or squamous cell carcinoma of the skin
 - Carcinoma *in situ* of the cervix or breast
 - Incidental histologic finding of prostate cancer (TNM stage of T1a or T1b)
7. Corrected QT interval using Fridericia's formula (QTcF) value $>$ 480 msec at screening; family or personal history of long QTc syndrome or ventricular arrhythmias including ventricular bigeminy at screening; previous history of drug-induced QTc prolongation or the need for treatment with medications known or suspected of producing prolonged QTc intervals on ECG.

8. Positive human immunodeficiency virus (HIV), hepatitis B virus (HBV) and known or suspected active hepatitis C virus (HCV) infection.
9. Hypersensitivity to thalidomide, lenalidomide, or dexamethasone (such as Steven Johnson Syndrome). Hypersensitivity, such as rash, that can be medically managed is allowable.
10. Peripheral neuropathy \geq Grade 2 despite supportive therapy.
11. Radiotherapy or systemic therapy (standard or an investigational or biologic anticancer agent) within 14 days of initiation of study drug treatment.
12. Current enrollment in another clinical study involving treatment and/or is receiving an investigational agent for any reason.
13. Inability or unwillingness to comply with birth control requirements or any of the POMALYST REMSTTM or RevAid[®] requirements (region-specific), per Appendix 9.3 and Appendix 9.4, respectively, or to the European Pomalidomide Pregnancy Prevention Risk Management Plans, per Appendix 9.5.

4.4. Source of Patients

This will be a multi-center study. Each study center is required to obtain Institutional Review Board (IRB)/Independent Ethics Committee (IEC) approval to conduct the study before enrollment of patients may commence. Patients at the study center meeting the entrance criteria, or referred to the study center will be eligible for enrollment.

4.5. Patient Identification and Registration

To ensure accurate and timely monitoring of patient enrollment, the following procedures will be implemented:

- Patients who are candidates for enrollment into the study will be evaluated for eligibility by the Investigator to ensure that the entrance criteria (see Sections 4.2 and 4.3) have been satisfied and that the patient is eligible for participation in this clinical study.
- The patient will be assigned a sequential and unique patient number. Once a patient number has been assigned, it cannot be reused.
- The Investigator or the Investigator's research staff will provide eligibility information to Acetylon. As confirmation, Acetylon will provide the Investigator with written verification of each patient's registration. No patient may be enrolled or begin treatment prior to Acetylon registration.
- Patients who are registered but not treated will be replaced. Patients who discontinue from the study before completing Cycle 1 for reasons other than DLT also are to be replaced.
- Investigators will be notified by Acetylon when enrollment in a given dose cohort is closed and enrollment into the next dose cohort can begin.
- Investigators will be notified by Acetylon if the study is placed on administrative hold, when it is completed, closed to further patient enrollment, or unexpected AEs occur.

4.6. Withdrawal and Replacement of Patients

Patients will be informed that they have the right to withdraw from the study at any time for any reason, without prejudice to their medical care. The Investigator also has the right to withdraw patients from the study for any of the following reasons:

- Non-adherence to the POMALYST REMSTTM or RevAid[®] Programs,
- Progressive Disease
 - Determination of PD requires two consecutive assessments of disease progression. There is no specific requirement for the timing of these two assessments,
- Occurrence of an unacceptable AE,
- Pregnancy,
- Patient requires use of an unacceptable concomitant medication,
- General or specific changes in the patient's condition unacceptable for further treatment in the judgment of the Investigator,
- Non-compliance,
- Patient withdrawal of consent,
- Patient no longer meets the protocol entrance criteria (see Sections 4.2 and 4.3),
- Sponsor request.

At the time of withdrawal, all study procedures outlined in the Schedule of Assessments (Table 1) post-treatment follow-up visit (i.e., pregnancy test for FCBP, pregnancy counseling, AE evaluation, assessment of second primary malignancy, etc.) should be completed if possible. The primary reason for a patient's withdrawal from the study is to be recorded in the electronic case report form (eCRF).

Patients who discontinue from the study for reasons other than DLT (e.g., non-compliance, patient request) before completing Cycle 1 will be replaced.

4.7. Patient Management

This study will be conducted on an outpatient basis.

Patients will be evaluated for study eligibility at screening, within 28 days before the first study drug dose. All patients must provide written informed consent before any samples are collected or evaluations are performed in this study. If patients have had recent scans, bone marrow biopsy, or blood test for other purposes prior to enrollment, these tests may be used for determination of eligibility if they were performed within the 28-day period before Baseline (C1D1, before study drug administration). Patients who are determined to be eligible will be enrolled in the study at Baseline. Patients will be evaluated at the study center on Days 1, 2, 8, 15, and 22 of Cycle 1. During Cycle 2, patients will be evaluated at the study center on Days 1 and 15. For all subsequent cycles, patients will be evaluated at the study center on Day 1. Patients who withdraw from the study are to be followed up either in person or by phone 30 days (\pm 3 days) after the last dose of study drug. If patients are treated with an alternate MM therapy before the 30 day visit, assessments for the 30 day visit should be performed prior to initiation of the alternate therapy.

Patients are to receive study treatment until development of PD or an unacceptable toxicity that cannot be managed by dose reduction alone precludes further treatment. Upon discontinuation from the study for PD or any other reason, patients will be assessed 3 times per year (e.g., April, August, and December), for up to 1 years for survival, subsequent anti-myeloma therapies, and monitoring of second primary malignancies as outlined in Table 1. SAEs will be collected from C1D1 through the first 30 days of follow-up. Subsequent therapies should be collected until death or end of the 1 year follow-up period. Survival follow up may be done via phone, when relevant. Patients who discontinue study treatment due to reasons other than PD will also be followed for efficacy assessments (see Section 6.2) until PD, death, or initiation of an alternate MM therapy, whichever occurs first.

Patients who have been contacted at least 3 times without success (at least 1 month apart) should be sent a certified letter. If no contact is established, the patient will be deemed lost to follow up. A similar process will be followed for patients being followed up by phone. All attempted contact should be documented in the patient's medical chart.

4.8. Safety Review Committee

An SRC will be involved in the conduct of this study. The SRC will be comprised of the Study Investigators, the Sponsor Medical Monitor, and the Safety Monitor. The SRC has the responsibility for monitoring the clinical study's progress and the safety of the participating patients. The SRC will evaluate study conduct during the course of the clinical study based upon data defined in the SRC Charter for this clinical study. Safety assessments will be conducted in real-time by the SRC after the first 3 patients have completed Cycle 1. Dose escalations or expansion of a dose cohort will occur only with full approval of the SRC.

The SRC will review safety data from all patients enrolled in each dose cohort to confirm any DLTs that were experienced and make a determination regarding enrollment in the next dose cohort. Each of the first 3 patients in the dose cohort must have completed Cycle 1 (28-day cycle) to be eligible for SRC review and for a decision to be made regarding enrollment into the next dose level. If a DLT necessitates enrollment of additional patients into a dose cohort, the SRC will review all of the safety data for that dose cohort after those additional patients have completed Cycle 1 through Day 21. Based on evaluation of the data, the SRC may decide that enrollment at an alternate starting dose or an intermediate dose level not specified in this protocol may take place. If this occurs, the IRB/IEC will be informed of the intermediate dose level(s) or alternate dosing regimen.

The SRC will also review all Phase 1b safety data to determine the recommended dose of ACY-1215 to be used in the Phase 2 segment of the study. The SRC may decide that enrollment at an intermediate starting dose or alternate dosing regimen not specified in this protocol may take place. If this occurs, the IRB/IEC will be informed immediately of the intermediate dose level(s) or alternate dosing regimen.

4.9. Independent Response Assessment Committee

The Independent Response Assessment Committee (IRAC) will be composed of 3 hematologists with expertise and experience in the diagnosis and management of multiple myeloma and a biostatistician. The IRAC will review, at ad hoc and scheduled meetings, all efficacy data in a blinded manner (independent of investigator-reported response) and provide verifiable and objective assessment of each patient's disease response. Patient data will be displayed using a unique number for each patient.

IRAC meetings will be convened when sufficient data becomes available for 30 enrolled patients, as well as prior final analysis, and intermittently as appropriate. The IRAC will determine disease response according to the following categories as specified in the IMWG (Appendix 9.5) and EBMT (Appendix 9.7) criteria. The IRAC will also make a disease response determination at 28-day intervals (study visits) up to and including the discontinuation from treatment visit.

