2.2.2. Secondary Endpoints

The secondary endpoints include the following:

Efficacy

Phase 1b and Phase 2:

- Time to response (TTR).
- Duration of response (DOR).
- Time to progression (TTP).
- Progression-free survival (PFS).

- Objective response to treatment as blindly assessed by the Central Adjudication Committee using IMWG criteria and dates of progressive disease (PD).

Safety

Phase 1b and Phase 2:

- Safety (type, frequency, and severity of AEs and relationship of AEs to study drug)

Pharmacokinetics

Phase 1b:

- Plasma levels of ACY-1215 to assess the single and multiple-dose PK of ACY-1215 in combination with pomalidomide and low-dose dexamethasone.
- Plasma levels of pomalidomide to assess the PK of pomalidomide in combination with ACY-1215 and low-dose dexamethasone.

Pharmacodynamics

Phase 1b:

- Exposure-response of ACY-1215 in combination with pomalidomide and low-dose dexamethasone, including biomarkers relating to intracellular protein acetylation.

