6.2.6. Assessment of Disease Response

Assessment of response will include measurement of serum M-protein by SPEP and UPEP, SFLC analysis (see Section 6.2.2) and immunofixation studies. Objective response, as assessed by site Investigators using the recently revised IMWG criteria has been chosen as the primary endpoint for this study. The IMWG criteria were developed by the International Myeloma Working group in order to provide uniform reporting requirements for studies conducted in MM and to enable consistent comparison of results across studies. Based on the EBMT, IMWG criteria have been expanded, clarified, and updated to provide a new comprehensive evaluation system to assess not only response but also the magnitude of response, length of response, and OS, (Appendix 9.5). Use of the IMWG criteria, the international standard for the assessment of response for MM studies, will ensure that data across all centers is evaluated consistently. Response will be assessed every cycle throughout study drug treatment, and at treatment discontinuation in both the Phase 1b and Phase 2 segments of the study. In addition to the site Investigators, an Independent Central Adjudication Committee will review the myeloma response data (i.e., laboratory data and radiographic data) to determine response to treatment and dates of PD for each study patient. Determination of PD requires two consecutive assessments of disease progression. There is no specific requirement for the timing of these two assessments.

Additional secondary endpoints of disease response will include TTR, DOR, TTP, and PFS. In addition, central laboratory data will be employed to maintain consistency in evaluation of efficacy endpoints.

Overall response rates utilizing either or both criteria will be reported in the clinical study report. Response to treatment will also be blindly assessed by the Central Adjudication Committee using IMWG criteria and dates of PD.

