Clinical relapse (Not used for TTP or PFS)	Clinical relapse requires one or more of: 
 Development of new soft tissue plasmacytomas or bone lesions on skeletal survey, magnetic resonance imaging, or other imaging Definite increase in the size of existing plasmacytomas or bone lesions. A definite increase is defined as a 50% (and at least 1 cm) increase as measured serially by the sum of the products of the cross-diameters of the measurable lesion Hypercalcemia (> 11.5 mg/dl [2.875 mmol/L]) Decrease in hemoglobin of ≥ 2 g/dl (1.25 mmol/L) Rise in serum creatinine by 2 mg/dl or more (≥ 177 mmol/L) Hyperviscosity

¹ All response categories require 2 consecutive assessments made at any time before the institution of any new therapy; all categories also require no known evidence of progressive or new bone lesions if radiographic studies were performed.

VGPR and CR categories require serum and urine studies regardless of whether disease at baseline was measurable on serum, urine, both, or neither. Radiographic studies are not required to satisfy these response requirements. Bone marrow assessments need not be confirmed. For PD, serum M-protein component increases of more than or equal to 1 g/dL are sufficient to define relapse if starting M-component is ≥ 5 g/dL.

- 2 Clarifications to IMWG criteria for coding CR and VGPR in patients in whom the only measurable disease is by serum FLC levels: CR in such patients indicates a normal FLC ratio of 0.26 to 1.65 in addition to CR criteria listed above. VGPR in such patients requires a $> 90\%$ decrease in the difference between involved and uninvolved FLC levels
- 3 Clarifications to IMWG criteria for coding PD: Bone marrow criteria for PD are to be used only in patients without measurable disease by M protein and by FLC levels; “25% increase” refers to M protein, FLC, and bone marrow results, and does not refer to bone lesions, soft tissue plasmacytomas, or hypercalcemia and the “lowest response value” does not need to be a confirmed value.

Source: adapted from [Rajkumar et al, 2011 \[50\]](#)

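### Section 4.9 ends the committee's 28-day response determinations at the treatment-discontinuation visit, in conflict with its own remit, the committee PD-date endpoint and the post-treatment efficacy follow-up

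*Combined protocol and SAP*

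**What the plan says.** Three parts of the protocol bear on how long the blinded committee follows each patient.

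- **Committee remit, Section 4.9.** The general remit is broad: "The IRAC will review, at ad hoc and scheduled meetings, all efficacy data in a blinded manner (independent of investigator-reported response". Meetings are to be held when data are sufficient for 30 enrolled patients, and then "as well as prior final analysis, and intermittently as appropriate". The section closes with the only sentence that sets a time window for determinations: "The IRAC will also make a disease response determination at 28-day intervals (study visits) up to and including the discontinuation from treatment visit".
- **Endpoint, Sections 2.2.2 and 6.2.6.** A secondary efficacy endpoint for both phases is "Objective response to treatment as blindly assessed by the Central Adjudication Committee using IMWG criteria and dates of progressive disease (PD". The synopsis and Section 6.2.6 describe the committee's task as being "to determine response to treatment and dates of PD for each study patient", with no on-treatment limit.
- **Follow-up, Section 4.7.** "Patients who discontinue study treatment due to reasons other than PD will also be followed for efficacy assessments (see Section 6.2) until PD, death" or alternate myeloma therapy, whichever comes first. The synopsis, Sections 3.1 and 6.2, and Table 1 footnote 1 say the same in substance, although Section 6.2 does not list death.

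On confirmation, footnote 1 of Appendix 9.6 states: "All response categories require 2 consecutive assessments made at any time before the institution of any new therapy". Sections 4.6 and 6.2.6 require two consecutive assessments for PD and set no timing between them.

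Section 4.9 calls the body the Independent Response Assessment Committee (IRAC). Sections 2.2.2 and 6.2.6 call it the Central Adjudication Committee. The documents do not say that the two are the same.

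**The concern.** A charter writer looking for a read schedule would find only the closing sentence of Section 4.9 and would stop by-visit reads at the discontinuation visit. A patient who stops for toxicity in stable disease or partial response and progresses two months later would then have an investigator PD date but no scheduled committee determination of that progression. A response first met at the discontinuation visit and confirmed at the next assessment would fall outside the window in the same way.

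The trial is single-arm and open-label, and the site investigators assess the primary endpoint. The blinded read is there to test those calls. If the two reads cover different follow-up, a disagreement between them may reflect the window and not the judgement. Ending the committee's PD dates when treatment stops would also amount to censoring at a moment that is rarely independent of prognosis. Section 7.6.7 gives no censoring rule for this case, and Section 7.4 rules out imputation.

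**Working it through.** The plan gives no figure for this point, so the check is first a reconciliation of text and then an illustration of size.

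**Step 1: the texts side by side.**

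| Question | Source | Answer |
|---|---|---|
| What data does the committee review? | 4.9, general remit | All efficacy data, with no cut-off |
| When are by-visit determinations made? | 4.9, last sentence | Every 28 days, ending at the discontinuation visit |
| For whom are committee PD dates needed? | Synopsis; 6.2.6 | Each study patient |
| When does efficacy follow-up end after a non-PD stop? | Synopsis; 3.1; 4.7; Table 1 footnote 1 | PD, death or alternate therapy |
| When must a response be confirmed? | Appendix 9.6, footnote 1 | Any time before new therapy |

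Four of the five answers run past treatment discontinuation. The second does not. Read literally, it leaves post-treatment assessments with no scheduled committee determination.

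**Step 2: how many patients could be affected.** The documents do not give the share of patients who stop for reasons other than PD. Assume 10%, 20% or 30%.

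- Of 66 evaluable: 66 × 0.10 = 6.6, 66 × 0.20 = 13.2, 66 × 0.30 = 19.8, so about 7 to 20.
- Of 86 evaluable: 86 × 0.10 = 8.6, 86 × 0.20 = 17.2, 86 × 0.30 = 25.8, so about 9 to 26.

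For these denominators the counts are upper bounds. Patients who die or start another therapy before PD have no PD date under either reading.

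**Step 3: illustrative effect on the median.** Inputs:

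- Median time to progression of 116 days, borrowed from the 16.6-week median PFS on pomalidomide plus dexamethasone in Section 1.1 (16.6 × 7 = 116.2). Using a PFS median for time to progression is itself an assumption.
- On-treatment progression is exponential, with rate λ = ln 2 / 116 = 0.00598 per day.
- A competing non-PD stop with rate μ, set so that a share f stops first: μ = λ f / (1 − f).
- After stopping, the progression rate is hλ with h = 1.5 or 2 (assumed).

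Censoring at the stop estimates the on-treatment curve, whose median is 116 days. Following every patient to PD gives

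S(t) = exp(−(λ+μ)t) + [μ / (λ + μ − hλ)] × [exp(−hλt) − exp(−(λ+μ)t)].

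Solving S(t) = 0.5:

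| f | μ per day | Median, h = 1.5 | Median, h = 2 | Overstatement (days) |
|---|---|---|---|---|
| 10% | 0.00066 | 114.1 | 112.6 | 1.9 to 3.4 |
| 20% | 0.00149 | 112.0 | 109.0 | 4.0 to 7.0 |
| 30% | 0.00256 | 109.6 | 105.1 | 6.4 to 10.9 |

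The overstatement is about 2 to 11 days, less than one 28-day assessment interval throughout.

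**The case against.** The strongest reply is that Section 4.9 does not stop the committee's review. It gives the committee all efficacy data at ad hoc and scheduled meetings, one of them before the final analysis. The by-visit sentence says the committee will also make these determinations, which reads as an addition to the general review. The synopsis and Section 6.2.6 assign PD dates without an on-treatment limit. All of this stands. A reader might infer that patients who stop for non-PD reasons can never receive a committee PD date, or that the committee never sees their later data. The documents do not support that. They leave it open, and one sentence points the wrong way.

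Three further points limit the concern.

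- **Confirmation.** A reader might infer that late confirmation is barred. Appendix 9.6 allows it up to the start of new therapy, so the bar comes only from the Section 4.9 window. Nor is a later assessment always available: none is planned for patients who stop because of PD, and Table 1 gives no column or interval for the others.
- **Other safeguards.** The committee is not the only check on site calls. Under Sections 3.1 and 6.2 a central laboratory analyses duplicate immunoglobulin, electrophoresis, immunofixation and free light chain samples and withholds the results from sites. Section 6.2.6 brings central laboratory data into the efficacy evaluation.
- **Censoring.** No passage states that committee PD dates are censored at treatment stop, and Section 7.6.7 does not name the committee as assessor for PFS or duration of response. The bias in the working is therefore conditional on how the window is applied.

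The inconsistency survives the reply. The general remit sets no schedule and the specific sentence does. If the committee is meant to read everything to PD, the limit serves no purpose. If the limit is meant, the endpoint cannot be delivered for these patients as scheduled.

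**Conclusion.** The concern holds as an internal inconsistency with a practical consequence. The Section 4.9 window conflicts with the committee's own remit, with the PD-date endpoint and with the efficacy follow-up. Applied as written, it leaves post-treatment progressions and late-confirmed responses without a scheduled committee determination, and it puts committee and investigator PD dates on different follow-up.

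The consequence is limited to the committee-assessed secondary endpoint; the investigator-assessed primary response analysis is untouched. The shift in the median is small. The larger loss would be missing PD dates and unconfirmed responses in a small trial. The size estimates depend on the assumed stop rates, exponential times, borrowed median and post-stop hazard ratios, none of which the documents supply for this trial. The correction is worth making because it is cheap and uses data already to be collected.

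**What to change.** In the last sentence of Section 4.9, and in the committee charter, replace the limit at the discontinuation visit with wording such as: at every efficacy assessment collected, including those after treatment discontinuation, until PD, death or start of another anti-myeloma therapy. The word collected is deliberate, because Table 1 sets no interval for these assessments.

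Add that the committee may use those assessments, where they exist, to confirm a response or PD first met at the discontinuation visit. State that the IRAC is the Central Adjudication Committee of Sections 2.2.2 and 6.2.6, if that is so. If the sponsor does intend determinations to end at discontinuation, the plan should say so in the endpoint definition and give the censoring rule.

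The change adds no visits or samples, and the committee already meets before the final analysis. The cost is slightly more data for it to read.
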